3.4.2 Screening and Inclusion

Patients written informed consent is to be obtained before any study related procedures are performed.

Approved candidates who consent to study participation will be considered as enrolled in the trial and are to be registered through the R&D UNICANCER eCRF (https://ecrf.icm.unicancer.fr/csonline). All enrolled patients will be assigned a unique identification number consisting of the letter P (for pembrolizumab) followed by 8 digits. The first 5 digits will identify the participating site and the next 3 the order in which the patient was included at the site (e.g. the third patient included at site 01001 will be assigned the number P01001-003). This number must be used as the sole patient identifier throughout the study especially for the identification of biological samples.

Baseline assessments are to be performed as described in Section 7.1. It is the responsibility of the Investigator to verify and confirm that and all inclusion and non-inclusion criteria are met prior to initiating study treatment.

Once patient eligibility is confirmed Investigators should submit a request for IP via completion of (at a minimum) the inclusion/exclusion criteria pages and registration form available on the R&D UNICANCER eCRF website (https://ecrf.icm.unicancer.fr/csonline/).

Investigators should also complete the remaining CRF pages pertaining to patient screening and baseline disease assessment prior to treatment initiation.

Confirmation of patient inclusion and dispatch of the IP will be transmitted by e-mail to both the investigator and the pharmacist within 24 hours of receipt of the required information. A delay of 72 hours (from time of request) should be anticipated for IP delivery to avoid inappropriate visit scheduling for the patient.

3.5 Procedure for Breaking the Randomization Code (Unblinding)

Not applicable

3.6 Trial Early Terminations/Stopping Rules and Patient Premature Discontinuation

3.6.1 Temporary Discontinuation and Definitive Termination of the Trial

The end of the trial is defined as the last follow-up visit of the last patient.

The trial can be suspended or stopped by the Sponsor after consultation with the Coordinating Investigator and Steering Committee or following a request by the respective Regulatory Authority and/or the responsible EC for the following reasons:

High frequency and/or unexpected severity of toxicity.

DOC43 Protocol ME EN v1.0 05-09-2014

- Insufficient patient recruitment.
- Insufficient quality of data collection.

3.6.2 Premature Trial/Patient Discontinuation Criteria

Patient treatment is planned to continue for a maximum of 24 months (or 35 cycles, whichever is longer), or until failure (i.e. disease progression, or death). Treatment may also be terminated early at the initiative of either the patient or the investigator for any reason that would be beneficial to the patient, including: unacceptable toxicity, intercurrent conditions that preclude continuation of treatment, or patient request.

The decision to discontinue a subject, is the responsibility of the treating physician and will not be delayed or refused by the Sponsor. The Investigator may contact the Sponsor/Coordinating Investigator prior to discontinuing a subject however, and forward appropriate supporting documents for review and discussion.

Patients participating in this trial protocol may withdraw their consent and exit the trial at any time without justification irrespective of their reason(s). Withdrawal of consent does not preclude the patient's right to receive alternative treatment (see Section 14.4).

Protocol n° UC-0105/1612 - version n°10.0, November 22, 2021

4 PATIENT SELECTION

4.1 Inclusion Criteria

Patients must meet all of the following criteria to be included in the study:

- 1. Patient information sheet and written informed consent form (PIS/ICF) signed.
- 2. Histologically confirmed diagnosis of a pathology corresponding to one of the following selected cancer types:
 - Rare sarcoma: Alveolar soft part sarcoma, Chordoma, Dedifferentiated chondrosarcoma, epithelioid sarcoma, sarcoma with loss of INI1, malignant rhabdoid tumours, myxoid liposarcoma, angiosarcoma of the scalp, radiation induced sarcomas. From the 51st patient included in this cohort, only the following histological types will be selected: Alveolar soft part sarcoma, Chordoma, SMARCA4-malignant rhabdoid tumours and Desmoplastic small-round-cell tumor.
 - Rare ovarian cancer: recurrent or relapsed; sex cord tumour, germ cell tumour (immature teratoma, non seminomatous germ cell & dysgerminoma), low-grade serous carcinoma, mucinous carcinoma, clear cell adenocarcinoma, small cell carcinoma, and carcinosarcoma with histological confirmation following review by members of the Tumeurs Malignes Rares Gynécologiques (TMRG) network (French rare gynaecological tumour group). From the 51st patient included in this cohort, only the following histological types will be selected: immature teratoma, low-grade serous carcinoma and ovarian small cell carcinoma hypercalcemic type (SCOOHT).
 - Primary central nervous system lymphoma: refractory primary intraocular and CNS lymphoma. From the 51st patient included in this cohort, only CNS lymphoma will be selected.
 - Rare thyroid cancer: differentiated thyroid carcinoma (Papillary, follicular, Hurthle cell (oncocytic), poorly differentiated thyroid carcinoma), medullary thyroid carcinoma, anaplastic thyroid carcinoma.
 - Rare malignant neuroendocrine tumour: poorly differentiated digestive tumours refractory
 after 2 lines of chemotherapy including cisplatin/carboplatin-etoposide (CDDP/carboVP16) and 5-Fluoro-uracile/irinotecan (FOLFIRI), poorly differentiated non digestive
 tumours refractory after 2 lines of chemotherapy including cisplatin/carboplatin-etoposide
 (CDDP/carbo-VP16) and any second line of chemotherapy, well differentiated tumours
 refractory after 4 lines of treatment including 2 lines of chemotherapy, everolimus and
 sunitinib, carcinoid tumours after 2 lines of treatment including Peptide Receptor
 Radionuclide Therapy (PRRT) or chemotherapy and everolimus.
 - Trophoblastic germ-cell tumour progressing after standard therapy.
 - Natural killer T-cell lymphoma: extranodal NK/T-cell lymphoma regardless of localization that is resistant or refractory to prior L-asparaginase therapy.
- 3. Metastatic disease or unresectable locally advanced malignancy that is resistant or refractory to standard therapy or for which standard therapy does not exist or is not considered appropriate by the Investigator.
- 4. Aged ≥ 18 years old for cohort 2 to 7 and aged ≥ 15 years old for patients included in cohort 1 (rare sarcoma).
- 5. Measurable disease defined:
 - according to RECIST v1.1 guidelines (Eisenhauer, 2009) for patients with solid tumours;
 - according to IPCG response criteria (Abrey, 2005) for patients with PCNSL;
 - according to RECIST v1.1 and / or abnormal levels of AFP, hCG and LDH for patients with germ-cell cancer;

- as focal uptake in at least one nodal or extra-nodal site with a Lugano 5-PS score of 4 or 5 (Cheson, 2014) for patients with NK/T-cell lymphoma,
- 6. Able to provide a FFPE biopsy sample of a metastatic site or primitive tumour tissue.

Note: Patients for whom suitable archived biopsy material is not available must be willing to undergo a biopsy of a tumour lesion prior to study entry, unless this is medically contraindicated (e.g. site inaccessible or patient safety concerns).

- 7. Patients must have a mandatory treatment-free interval of at least 21 days following previous systemic anti-cancer treatments.
- 8. Patients who have received previous systemic anticancer treatment and/or radiotherapy should have recovered from any treatment related toxicity, to a level of ≤ grade 1 (according to NCI-CTCAE criteria, v 4.0, Appendix 5) with the exception of Grade 2 alopecia.
- 9. Adequate hematologic function (absolute neutrophil count [ANC] \geq 1.0 x10⁹/L, platelets \geq 100 x10⁹/L, haemoglobin \geq 9 g/dL) measured within 14 days of treatment initiation unless due to lymphoma associated haemophagocytic lymphohistiocytosis (HLH).
- 10. Adequate renal function (creatinine clearance ≥ 50 mL/min using the MDRD or CKD EPI method) measured within 14 days of treatment initiation.
- 11. Adequate hepatic function (serum bilirubin ≤ 1.5 x the reference upper limit of normal (ULN) unless due to Gilbert's syndrome; ASAT and ALAT ≤ 3 xULN) measured within 14 days of treatment initiation unless due to lymphoma associated HLH. For patients with documented liver metastasis ASAT/ALAT ≤ 5x ULN is acceptable.
- 12. Strictly normal blood levels of calcium and magnesium, measured within 14 days of treatment initiation.
- 13. Eastern Cooperative Oncology Group (ECOG) Performance Status of ≤ 1 (Oken, 1982; Appendix 6).
- 14. Estimated life expectancy ≥ 90 days.
- 15. Patients who are sexually active must agree to use a medically accepted method of contraception (e.g. implants, injectables, combined oral contraceptives, some intrauterine devices or vasectomized partner, for participating women; condoms for participating men) or practice complete abstinence, beginning 14 days before the first administration of IP, while on treatment and for at least 5 months after the last administration of IP for female patients, and 7 months after the last administration of IP for male patients.
- 16. Women of childbearing potential must have a negative urine or serum pregnancy test within 72 hours prior to the first administration of IP. If urine test results are positive or cannot be confirmed as negative, a serum pregnancy test will be required.
- 17. Women who are breastfeeding should discontinue nursing prior to the first administration of IP and for at least 120 days after the last administration of IP.
- 18. Patients must be affiliated to a Social Security System or equivalent.

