10.2.1 Analysis of the Primary Endpoint

The primary endpoint in this study is objective response rate per cohort, defined as the percentage of patients in each cohort with a CR or PR, measured at the first scheduled disease assessment following study treatment initiation (Day 84, \pm 7 days) as assessed by the IRC according to RECIST v1.1, or

RECIST v1.1 combined with biomarker assessment, or IPCG response criteria or the 'Lugano' response using the FDG-PET-CT 5-PS and assessment of EBV load.

Results will be expressed as a percentage of the analysis population with a 95% exact confidence interval.

Patients who withdraw from the study prior to this time point or who have non-evaluable disease will be considered as 'non-responders' in this analysis.

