Appendix 2: Response Criteria for Germ-Cell Cancer

Response will be assed via a combination of RECIST v1.1 and assessment of evolution of biomarker levels (alpha-fetoprotein [AFP] and human chorionic gonadotropin [hCG] and lactate dehydrogenase [LDH]) in the blood, as follows:

Response criteria:

- a) Target lesions (according to RECIST v1.1, see Appendix 1)
 - Complete Response (CR): Disappearance of all target lesions. Any pathological lymph nodes (whether target or non-target) must have reduction in short axis to <10 mm

Warning: lymph nodes identified as target lesions should always have the actual short axis measurement recorded (measured in the same anatomical plane as the baseline examination), even if the nodes regress to below 10 mm on trial. This means that when lymph nodes are included as target lesions, the 'sum' of lesions may not be zero even if complete response criteria are met, since a normal lymph node is defined as having a short axis of <10 mm. In order to qualify for CR, each node must achieve a short axis <10 mm.

- **Partial Response (PR):** At least a 30% decrease in the sum of diameters of target lesions, taking as reference the baseline sum diameters.
- **Progressive Disease (PD):** At least a 20% increase in the sum of diameters of target lesions⁵, taking as reference the smallest sum on trial (this includes the baseline sum if that is the smallest on trial). In addition to the relative increase of 20%, the sum must also demonstrate an absolute increase of at least 5 mm. (Note: the appearance of one or more new lesions is also considered progression).

Warning: when a progression is recorded with respect to the Nadir but there is a response with respect to baseline, progression must be considered.

• **Stable Disease (SD):** Neither sufficient shrinkage to qualify for PR nor sufficient increase to qualify for PD, taking as reference the smallest sum diameters while on trial.

b) Non-target lesions (according to RECIST v1.1, see Appendix 1)

- Complete Response (CR): Disappearance of all non-target lesions. All lymph nodes must be non-pathological in size (<10 mm short axis).
- Non-CR/Non-PD: Persistence of one or more non-target lesion(s)
- **Progressive Disease (PD):** Unequivocal progression (see comments below) of existing non-target lesions⁶. (Note: the appearance of one or more new lesions is also considered progression).

c) Biomarkers

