- Complete Response (CR): Normalisation of all 3 tumour markers to within expected ranges.
- Non-CR/Non-PD: Maintenance of at least one tumour marker level above the normal limits.
- **Progressive Disease (PD):** Two consecutive elevations of any of the tumour markers (i.e. consistent increase in the level measured between 3 consecutive samples)

⁵ Except when pathological evidence of a growing teratoma syndrome is provided Protocol n° UC-0105/1612 - version n°10.0, November 22, 2021

Page 96 / 105

Overall response:

Target lesions	Non-target lesions	New lesions	Biomarkers	Overall response
CR	CR	No	CR	CR
CR	CR	No	Non CR/Non PD	PR
CR	CR	No	Not evaluated	PR
CR	Non CR/Non PD	No	CR	PR
CR	Non CR/Non PD	No	Non CR/Non PD	PR
CR	Non CR/Non PD	No	Not evaluated	PR
CR	Not evaluated	No	CR	PR
CR	Not evaluated	No	Non CR/Non PD	PR
CR	Not evaluated	No	Not evaluated	PR
PR	Non PD or NE	No	Non PD or NE	PR
SD	Non PD or NE	No	Non PD or NE	SD
Not evaluated	Non PD	No	Non-PD	Not-evaluable
PD	No change	Yes or No	No change	PD
No change	PD	Yes or No	No change	PD
No change	No change	Yes or No	PD	PD
No change	No change	Yes	No change	PD

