 total protein may have prognostic importance, the value of CSF total protein after therapy is unknown.
- At the time a CR is determined, the patient should have discontinued use of all corticosteroids for at least 2 weeks. Rare exceptions may be made for those patients receiving corticosteroids for another diagnosis (eg, panhypopituitarism).

Unconfirmed complete response (CRu) includes those patients who fulfill the criteria for CR with the following features/limitations:

- Any patient who fulfills all criteria for CR but continues to require corticosteroid therapy at any dose should be considered an unconfirmed CR. This is critical because corticosteroids may be oncolytic in treating occult tumor. In addition, corticosteroids may decrease gadolinium enhancement on MRI.
- Some patients will have a small but persistent enhancing abnormality on MRI related to biopsy or focal hemorrhage. It is often difficult to ascertain whether this represents a residual nidus of tumor or scar tissue. Adjunctive radiologic studies such as single-photon emission computed tomography or positron emission tomography may be helpful, but often the nature of these abnormalities may only be determined by observing the patient with serial scans. If the type of abnormality does not change

or slowly involutes over time without therapy and corticosteroids, it is reasonable to categorize it as a CR.

 Patients with a persistent minor abnormality on follow-up ophthalmologic examination (persistent nonmalignant cells in the vitreous, alteration of the retina/optic nerve that is not consistent with tumor infiltration) may be considered a CRu if this abnormality is unlikely to represent ocular lymphoma.

Partial response (PR) requires all of the following:

- A ≥ 50% decrease in the contrast-enhancing lesion seen on MRI as compared with baseline imaging.
- Corticosteroid dose is irrelevant to the determination of PR.
- Ophthalmologic examination should show a decrease in the vitreous cell count or retinal/optic nerve
 cellular infiltrate but may continue to show persistent malignant or suspicious cells. Color photos of
 the posterior pole of the eye should be obtained to document improvement in retinal/optic nerve
 infiltrates.

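### Criterion 5 lets germ-cell patients into Cohort 6 on markers alone, but Appendix 2 gives them no defined row leading to a response

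*Protocol*

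**What the plan says.** **Entry.** Section 4.1, criterion 5, repeated in the synopsis, defines measurable disease in this cohort as "according to RECIST v1.1 and / or abnormal levels of AFP, hCG and LDH for patients with germ-cell cancer". The 'or' limb admits patients whose disease is shown only by markers.

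**Response.** Appendix 2 scores target lesions, non-target lesions, new lesions and markers, then combines them in a table. Target PR is "At least a 30% decrease in the sum of diameters of target lesions, taking as reference the baseline sum diameters". Markers have three categories and no PR: CR is "Normalisation of all 3 tumour markers to within expected ranges", Non-CR/Non-PD is "Maintenance of at least one tumour marker level above the normal limits", and PD is "Two consecutive elevations of any of the tumour markers (i.e. consistent increase in the level measured between 3 consecutive samples". The one row with unassessed target lesions and no progression reads "Not evaluated Non PD No Non-PD Not-evaluable".

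**Scoring.** Section 10.2.1 says that patients "who have non-evaluable disease will be considered as 'non-responders' in this analysis". Section 10.5 analyses all included patients in their assigned cohort.

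**Progression.** Section 7.2.8.2 defines germ-cell progression as either the same three-sample marker rise or RECIST progression, with an exception for growing teratoma syndrome.

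**The concern.** The eligibility rule and the response rule do not describe the same patients. Someone admitted because markers are the measure of disease has no baseline sum of diameters. The table then offers no row in which normalisation of the markers, on its own, becomes a response. If such patients fall into the Not-evaluable row, they stay in the denominator of the primary endpoint and cannot enter the numerator. The same scoring feeds the interim futility look, which starts at 10 patients.

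A second, smaller problem is that the marker-progression rule does not fit the rest of Appendix 2. This touches both the response classification and PFS.

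**Working it through.** The protocol states no expected ORR for Cohort 6 and no marker-only share, so there is no planned figure to reproduce.

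**Step 1: trace the table for a patient with no target lesion.**

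| Target-lesion entry | Overall responses reachable without PD |
|---|---|
| CR | CR or PR |
| PR | PR |
| SD | SD |
| Not evaluated | Not-evaluable |

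No row is labelled for absent target lesions. Two readings are possible:

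- *Absent = Not evaluated.* The result is Not-evaluable, hence non-response, even if all three markers normalise.
- *Absent = target CR.* The rows with target CR and markers Non-CR/Non-PD give PR. A patient whose markers stay abnormal but do not progress would be scored a responder.

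**Step 2: size under the first reading.** Let p be the true response rate and f the marker-only share (assumed). Patients are taken as independent, with p the same in both groups.

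Observed ORR = p(1 - f), and P(0/10) = (1 - observed ORR)^10.

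| p | f | Observed ORR | P(0/10) |
|---|---|---|---|
| 0.20 | 0 | 0.20 | 0.80^10 = 10.7% |
| 0.20 | 0.1 | 0.18 | 0.82^10 = 13.7% |
| 0.20 | 0.2 | 0.16 | 0.84^10 = 17.5% |
| 0.20 | 0.3 | 0.14 | 0.86^10 = 22.1% |
| 0.20 | 0.4 | 0.12 | 0.88^10 = 27.9% |
| 0.30 | 0 | 0.30 | 0.70^10 = 2.8% |
| 0.30 | 0.3 | 0.21 | 0.79^10 = 9.5% |

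**Step 3: does 0/10 trigger futility?** Section 10.3 sets p0 = 0.10 and allows a Jeffreys or a uniform prior. The synopsis gives 85% confidence; section 10.3 gives only a usual range of 0.8 to 0.9.

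- Jeffreys, posterior Beta(0.5, 10.5): P(p < 0.10) = 0.858, which exceeds 0.85.
- Uniform, posterior Beta(1, 11): P(p < 0.10) = 1 - 0.9^11 = 0.686, which does not.

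Applying the futility rule at 10, 15, ..., 50 patients with true p = 0.20, the probability of ever crossing goes from 0.112 (f = 0) to 0.255 (f = 0.3) with Jeffreys, and from 0.015 to 0.080 with uniform.

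**Step 4: direction under the second reading.** If a share s of marker-only patients merely do not progress, or do better, observed ORR = p(1 - f) + fs. This exceeds p whenever s > p. The protocol gives no value for s.

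**Step 5: marker progression set beside the other marker rules.**

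- Marker CR refers to the normal range. Marker PD refers only to direction over three samples, with no size of rise and no reference to the normal limit. Three rising values that all lie within range satisfy both definitions.
- The PR row for target lesions in PR requires markers that are not PD, or not evaluated. The row for marker PD pairs it with lesions marked as No change. Lesion PR with marker PD therefore has no row, although section 7.2.8.2 makes it progression.

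**The case against.** **A reader might infer that marker-only patients can never be scored as responders.** The text does not go that far. It has no row for absent target lesions, so equating them with Not evaluated is the natural reading but not a stated one. Section 6.1.1 also defers the committee's methods to an IRC charter that is not shown. This objection stands against certainty about the direction of bias, but not against the gap itself: the two readings lead to opposite errors and the protocol does not choose. Nor is the charter a full answer, because the interim looks use the investigators' assessment.

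**The marker-only group may be small.** Read strictly, the criterion could require AFP, hCG and LDH all to be abnormal. This stands, and it is why f is shown only as an assumed range.

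**The futility harm is conditional.** It depends on the prior, and the synopsis speaks only of potential closure. This stands.

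**A reader might infer that laboratory noise would turn a large part of the true responders into progressions.** The documents do not support that. Such a calculation needs exchangeable values without ties and independent variation of three markers. Falling markers in a responder make a three-sample rise much less likely, and tied values at a detection limit are not a rise. What remains is the inconsistency in step 5.

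**A reader might see the same loss in PCNSL**, because Appendix 3 says "Any patient who fulfills all criteria for CR but continues to require corticosteroid therapy at any dose should be considered an unconfirmed CR" while the endpoint counts CR or PR. In general it does not follow. Appendix 3 makes steroid dose irrelevant to PR, so such a patient normally qualifies as PR anyway. The exception is primary leptomeningeal lymphoma, where Appendix 3 does not recognise PR.

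**Conclusion.** The concern holds as a mismatch between criterion 5 and Appendix 2 that leaves the primary endpoint undefined for marker-only patients in Cohort 6. On the more natural reading, ORR is understated by the factor (1 - f): at p = 0.20 and f between 0.1 and 0.4 it falls to between 0.18 and 0.12. These figures rest on an assumed f, an assumed p and a common response rate in both groups. A 0/10 result reaches the 85% futility level only with the Jeffreys prior. On the other reading the bias is upward, by an amount the documents do not allow one to compute. The effect is confined to one of seven cohorts.

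The marker-progression point holds only as a contradiction within the protocol. For PCNSL, all that remains is to clarify the status of CRu where PR is not recognised.

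**What to change.** **Appendix 2.** Add rows for patients with no target lesion at baseline, so that overall response is classified from markers, non-target lesions and new lesions. Score marker normalisation with no new lesion as a response, and state whether it is CR or PR. Use the same rows in the IRC charter and for the investigators' assessment at interim looks. Report the Cohort 6 ORR with and without these patients.

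**Reconciliation.** Section 7.2.8.2 and Appendix 2 must agree on how in-range rising markers are classified and on the overall response when lesions are in PR and markers in PD. Because progression ends treatment, the rule itself is for the sponsor to set; no threshold is proposed here.

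**Appendix 3.** State in one sentence how CRu counts in primary leptomeningeal lymphoma.

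**Cost.** The protocol already collects the markers, imaging and lesion status, so no new assessment is needed. The drawback is that marker-only responses are not radiological, hence the two ORR figures. This is also a change to primary-endpoint scoring in version 10.0 of an open-label trial, so the amendment should give its reason and be settled without reference to Cohort 6 results.

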- 9. Adequate hematologic function (absolute neutrophil count ≥ 1.0 x10⁹/L, platelets ≥ 100 x10⁹/L, haemoglobin ≥ 9 g/dL) measured within 14 days of treatment initiation unless due to lymphoma associated haemophagocytic lymphohistiocytosis (HLH).
- 10. Adequate renal function (creatinine clearance ≥ 50 mL/min using the MDRD or CKD EPI method) measured within 14 days of treatment initiation.
- 11. Adequate hepatic function (serum bilirubin ≤ 1.5 xULN unless due to Gilbert's syndrome; aspartate aminotransferase [ASAT] and alanine aminotransferase [ALAT] ≤ 3 xULN) measured within 14 days of treatment initiation unless due to lymphoma associated HLH. For patients with documented liver metastasis ASAT/ALAT ≤ 5x ULN is acceptable.
- 12. Strictly normal blood levels of calcium and magnesium, measured within 14 days of treatment initiation.
- 13. Eastern Cooperative Oncology Group Performance Status of ≤ 1.
- 14. Estimated life expectancy ≥ 90 days.
- 15. Patients who are sexually active must agree to use a medically accepted method of contraception (e.g. implants, injectables, combined oral contraceptives, some intrauterine devices or vasectomized partner, for participating women; condoms for participating men) or practice complete abstinence, beginning 14 days before the first administration of IP, while on treatment and for at least 5 months after the last administration of IP for female patients, and 7 months after the last administration of IP for male patients.
- 16. Women of childbearing potential must have a negative urine or serum pregnancy test within 72 hours prior to the first administration of IP. If urine test results are positive or cannot be confirmed as negative, a serum pregnancy test will be required.
- 17. Women who are breastfeeding should discontinue nursing prior to the first administration of IP and for at least 120 days after the last administration of IP.

18. Patients must be affiliated to a Social Security System or equivalent.

EXCLUSION CRITERIA:

Patients meeting **any** of the following criteria will be excluded from participation in the study:

- 1. Prior treatment with an anti-PD1 or anti-PD-L1 antibody.
- 2. Eligible to participate in a clinical trial of an alternative anticancer therapy targeting their disease, which is open to accrual in France.

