5.11.2 Contraception

Patients should be informed that pembrolizumab may have adverse effects on a foetus *in utero*. Furthermore, it is not known if pembrolizumab has transient adverse effects on the composition of sperm. All patients of reproductive potential must agree to use (or have their partner use) a medically accepted form of contraception¹ during heterosexual activity, or practice abstinence² from heterosexual activity for the period beginning at least 14 days prior to their first IP administration, during the treatment period, and for at least 5 months after their last dose of IP for female patients, and 7 months after the last administration of IP for male patients. If there is any question that a patient of reproductive potential will not reliably comply with the requirements for contraception, that patient should not be entered into the study.

Acceptable methods of contraception¹ are:

- Single method (one of the following is acceptable):
 - o intrauterine device
 - o vasectomy of a female subject's male partner
 - o contraceptive rod implanted into the skin
- Combination method (requires use of two of the following):
 - o diaphragm with spermicide (cannot be used in conjunction with cervical cap/spermicide)
 - o cervical cap with spermicide (nulliparous women only)
 - o contraceptive sponge (nulliparous women only)
 - o male condom or female condom (cannot be used together)
 - hormonal contraceptive: oral contraceptive pill (oestrogen/progestin pill or progestinonly pill), contraceptive skin patch, vaginal contraceptive ring, or subcutaneous contraceptive injection

For this trial, male subjects will be considered to be of non-reproductive potential if they have azoospermia (whether due to having had a vasectomy or due to an underlying medical condition). Female subjects will be considered of non-reproductive potential if they are either:

- 1. Postmenopausal (defined as at least 12 months with no menses without an alternative medical cause; in women < 45 years of age a high follicle stimulating hormone (FSH) level in the postmenopausal range may be used to confirm a post-menopausal state in women not using hormonal contraception or hormonal replacement therapy. In the absence of 12 months of amenorrhea, a single FSH measurement is insufficient.);
- 2. OR, have had a hysterectomy and/or bilateral oophorectomy, bilateral salpingectomy or bilateral tubal ligation/occlusion, at least 6 weeks prior to screening;

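### Criterion 15 and the contraception checks give the pill, injectables and male condoms as examples of an accepted method, but Section 5.11.2 does not accept the pill, subcutaneous injection or condom alone

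*Protocol*

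**What the plan says.** **Criterion 15.** In Protocol 4.1, sexually active patients "must agree to use a medically accepted method of contraception (e.g. implants, injectables, combined oral contraceptives, some intrauterine devices or vasectomized partner"), with condoms as the example for men and complete abstinence as the alternative. The synopsis version opens with the same requirement, "must agree to use a medically accepted method of contraception", and gives the same examples.

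**Scheduled checks.** Flow-chart note 12 (synopsis, part H), 7.1 (screening) and 7.2.1 (Cycle 1 Day 1) have the site verify an acceptable form of contraception against the same list.

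**Section 5.11.2.** It states that "All patients of reproductive potential must agree to use (or have their partner use) a medically accepted form of contraception" or practise abstinence, and then lists what is acceptable. Three methods may be used alone: an intrauterine device, vasectomy of a female patient's male partner, and an implanted rod. The remainder come under "Combination method (requires use of two of the following"). That group includes "male condom or female condom (cannot be used together") and "hormonal contraceptive: oral contraceptive pill (oestrogen/progestin pill or progestinonly pill), contraceptive skin patch, vaginal contraceptive ring, or subcutaneous contraceptive injection". The section also says that a patient whose reliable compliance with these requirements is in any question should not be entered.

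**Section 3.4.2.** Before treatment the investigator must "verify and confirm that and all inclusion and non-inclusion criteria are met prior to initiating study treatment", and should then "submit a request for IP via completion of (at a minimum) the inclusion/exclusion criteria pages and registration form". It does not mention 5.11.2.

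**The concern.** Criterion 15 and 5.11.2 state one obligation in nearly the same words and over the same period: from 14 days before the first dose until 5 months (women) or 7 months (men) after the last. They differ on what satisfies it. The looser wording stands where eligibility is recorded and contraception is verified. The stricter wording stands in a later section to which those places do not point.

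What is at stake is protection against foetal exposure, since 5.11.2 warns that pembrolizumab may harm a foetus in utero. A site that works from the entry criterion and the two checks as written would accept less protection than 5.11.2 requires. Monitors would also have two standards against which to judge the same patient.

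**Working it through.** No formula applies, and the plan gives no figure to reproduce. The check sets the two texts side by side.

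**Step 1. Each method named in criterion 15 against 5.11.2.**

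| Method in criterion 15 | Status in 5.11.2 |
|---|---|
| Implant | Accepted alone (implanted rod) |
| Some intrauterine devices | Accepted alone |
| Vasectomised partner (women) | Accepted alone |
| Combined oral contraceptive | Two-method combination only |
| Injectable | Subcutaneous injection: two-method combination only; other injectables not listed |
| Condom (men) | Two-method combination only |

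Count: 6 methods named, 3 accepted alone, 6 − 3 = 3 not accepted alone. This counts list entries, not patients.

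**Step 2. Places that carry the looser list.** Criterion 15 in 4.1, criterion 15 in the synopsis, flow-chart note 12, 7.1 and 7.2.1 = 5. References to 5.11.2 in them: 0. Mentions of a second method: 0.

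**Step 3. Does the illustrative form of the list reconcile the texts?** No. A list of examples may be incomplete, but each example should satisfy the rule it illustrates. Three of these do not unless something is added to them.

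**Step 4. Who falls between the two texts.** Take a woman of reproductive potential on the combined pill whose partner uses nothing, or a man using condoms whose partner uses nothing. Each meets criterion 15 and both scheduled checks. Neither meets 5.11.2.

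**Step 5. Ways to comply.**
- *Add a second method.* The combination group has 5 categories: diaphragm with spermicide, cervical cap with spermicide, sponge, condom, hormonal. A user of one has at most 5 − 1 = 4 others, and fewer in practice because the cap and sponge are restricted to nulliparous women. For a man using condoms, all 4 are used by the female partner.
- *Use an accepted single method.* The patient may switch to one. Because 5.11.2 allows the partner to use the method, a man whose partner has an intrauterine device or implanted rod appears to comply already.
- *Otherwise.* If reliable compliance is in question, 5.11.2 says not to enter the patient.

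**The case against.** The best defence is that 5.11.2 is the operative definition. It is the section devoted to contraception, it uses mandatory language, and it has its own entry rule. Investigators commit to conducting the trial as the protocol specifies (14.8). A site that applies 5.11.2 does not breach criterion 15, so this is a loose summary beside a strict definition and not a pair of rules that cannot both be met. Criterion 15 also never says outright that one listed item is enough. Other safeguards remain: a negative pregnancy test within 72 hours before the first dose, removal from the study on pregnancy, and pregnancy reporting.

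Much of this stands. From 3.4.2 a reader might infer that sites apply only criterion 15 at entry, or that the protocol as a whole permits entry on the looser standard. The documents do not support that, because 5.11.2 also governs entry. A reader might equally infer that every affected patient must be excluded; 5.11.2 leaves room to add a method or change to an accepted one.

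The defence does not remove the mismatch. The natural reading of the examples is that each is an accepted method, and nothing in the five places sends the site to the section that says otherwise. Pregnancy testing and reporting detect or follow up a pregnancy; they do not replace contraception.

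**Conclusion.** The inconsistency is real. Three of the six methods named in criterion 15 are insufficient alone under 5.11.2, and the looser list appears in five places without a reference to the stricter one. Its reach is limited to patients of reproductive potential who rely on the pill, an injectable or condoms alone, with no other accepted method used by patient or partner. The protocol does not say how many that is, and 3 of 6 must not be read as a share of patients.

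This rests on reading criterion 15's injectables as including the subcutaneous injection of 5.11.2. Any other injectable is absent from 5.11.2, which widens the gap.

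It is a safety and eligibility wording problem. It does not touch the primary endpoint, the cohort stopping rules, the analysis populations or any statistical result. It should be corrected because sites may otherwise verify the wrong standard.

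**What to change.** In criterion 15 (4.1 and synopsis), flow-chart note 12, 7.1 and 7.2.1, replace the example lists with: a single method or a two-method combination listed in Section 5.11.2, used by the patient or partner. Keep the abstinence option. A patient now relying on one of the three methods alone may add a second method or switch to an accepted single method, by patient or partner, and is not entered if reliable compliance is in question.

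If the sponsor intends and can justify single-method use of the pill, injection or condom, amend 5.11.2 instead, so that one rule applies throughout.

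The cost is a wording amendment in five places, or in 5.11.2 alone. No new procedure, visit or analysis is needed.
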